9.2 Surgical Resection

Approximately 4 weeks (+/- 2 weeks) after the completion of the neoadjuvant treatment, patients will undergo standard of care operative exploration and complete extirpative surgery. Operative planning will be based on the original review of the patients' initial (i.e. pre-treatment) staging CT or MRI scan and the scan obtained after completion of the neoadjuvant protocol. All patients will undergo two modalities of operative exploration for occult metastatic disease undetectable with conventional cross-sectional imaging. Prior to laparotomy, patients will undergo a formal two-port staging laparoscopy to exclude the presence of occult metastatic disease involving the liver or peritoneal surfaces. Suspicious nodules possibly representing metastatic disease will be biopsied to confirm a pathologic diagnosis of metastatic pancreatic adenocarcinoma. Proof of metastatic cancer (i.e. stage IV cancer) will exclude patients from operative resection of the primary pancreatic cancer. In the absence of metastatic disease detectable with staging laparoscopy, patients will undergo a formal laparotomy with abdominal exploration to exclude occult metastatic disease involving the peritoneal surfaces or liver.

In the absence of occult metastatic disease, patients will undergo the planned operative procedure to resect the primary pancreatic adenocarcinoma completely. Based on preoperative imaging,

patients will undergo either a pancreatoduodenectomy (PD) or distal pancreatectomy and splenectomy (DPS). PD will be performed for patients with head and/or neck of pancreas cancers. DPS will be performed for patients with body and/or tail of pancreas cancers. PD and DPS will be performed according to standardized techniques which are employed routinely at Indiana University Hospital.

All margins of resection will be sampled intraoperatively to ensure complete clearance. For PD, the neck of pancreas and bile margins will be reviewed with frozen section histopathologic analysis. For DPS, the proximal pancreatic margin (i.e. body or neck of pancreas) will be reviewed intraoperatively. Final margin status (R0 versus R1) of the resected specimens will be recorded in addition to the intraoperative margin status assessments.

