14.3 Statistical analysis plan

Primary Outcome:

- Pathologic complete response: the proportion of the 48 patients having a pathologic complete response with a 95% confidence interval (using normal approximation) will be calculated.

Secondary Outcomes:

- *Safety:* Adverse events of grades 3, 4, 5 by the CTCAE v4.3 criteria for each category listed in section 2.1.6 will be summarized. The proportion of patients with each category of AE will be calculated with a 95% confidence interval. After the enrollment of the first 20 patients, we will evaluate the rate of surgical resection. If >6 patients are not able to proceed with surgery due to excessive toxicity or progression (not including occult metastatic peritoneal disease that was found during surgery and not on imaging) the study will discontinue due to unacceptable toxicity.

- *Ability of patients to undergo surgical resection after receiving neoadjuvant FOLFIRINOX*: the proportion of patients who are able to go through surgery among those who have resectable tumor will be calculated accompanied with a 95% confidence interval.
- *Rate of resectability* will be evaluated by determining the proportion of patients who are able to undergo surgery with resection of their primary tumor (R0 vs R1) resection. A 95% confidence interval will be constructed for the rate.
- *Disease free survival (DFS)*: DFS is defined as time from registration to evidence of tumor recurrence (including clinical deterioration related to the underlying pancreatic cancer, as assessed by the investigator) or death from any cause. Kaplan-Meier curve for DFS will be plotted. Median DFS time will be calculated accompanied with a 95% confidence interval.
- *Overall survival*: time from registration to death for 48 patients with right censoring will be analyzed using Kaplan-Meier estimate. Median survival time will be obtained accompanied with a 95% confidence interval.
- *Objective response rate*: proportion of patients with complete responses (CR) or partial responses (PR) after 4 cycles of FOLFIRINOX treatment will be constructed with a 95% confidence interval.
- *Disease control rate*: Proportion of patients with complete responses (CR), partial responses (PR), or stable disease (SD) after 4 cycles of FOLFIRINOX treatment will be obtained with a 95% confidence interval.

Tertiary Outcomes:

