14.4 Criteria for stopping study

The study will be discontinued if 25-30% of patients are unable to complete surgery due to toxicity. Analysis will be conducted after the first 20 patients are enrolled onto the study. If >6 patients are not able to proceed with surgery due to excessive toxicity the study will discontinue due to unacceptable toxicity.

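### Section 14.3's stopping count excuses imaging-occult peritoneal metastases found at surgery but not liver ones, and Section 14.4 gives a conflicting version in which neither counts

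*Combined protocol and SAP*

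**What the plan says.** Three places in the combined protocol and SAP bear on this.

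- **Section 14.3, Safety.** The look is described as "After the enrollment of the first 20 patients, we will evaluate the rate of surgical resection". The trigger is "If >6 patients are not able to proceed with surgery due to excessive toxicity or progression", and one category is taken out of the count: "not including occult metastatic peritoneal disease that was found during surgery and not on imaging". The liver is not mentioned.
- **Section 9.2.** Before laparotomy, "patients will undergo a formal two-port staging laparoscopy to exclude the presence of occult metastatic disease involving the liver or peritoneal surfaces". If that is clear, there follows a "formal laparotomy with abdominal exploration to exclude occult metastatic disease involving the peritoneal surfaces or liver". The consequence does not depend on site: "Proof of metastatic cancer (i.e. stage IV cancer) will exclude patients from operative resection of the primary pancreatic cancer".
- **Section 14.4.** The threshold is restated with a narrower cause: "If >6 patients are not able to proceed with surgery due to excessive toxicity the study will discontinue due to unacceptable toxicity". There is no progression term and no exclusion. The same section also says: "The study will be discontinued if 25-30% of patients are unable to complete surgery due to toxicity".

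No section extends the 14.3 exclusion to the liver, explains why it is limited to the peritoneum, or says whether 14.3 or 14.4 prevails.

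**The concern.** Take two patients with clear pre-operative imaging who have the same laparoscopy. One has a liver deposit and the other a peritoneal deposit, and neither is resected. On the literal wording of 14.3, the first can count towards closing the study and the second cannot. Section 9.2 draws no such distinction.

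The result matters because the count decides whether the trial continues, and closure under the rule is attributed to toxicity. A metastasis that imaging missed is not toxicity. The trigger is 7 of 20, so one or two patients classified either way can settle it. If the wording stays as it is, whoever conducts the look must decide how to classify an occult liver case after seeing it, and must also choose between 14.3 and 14.4. A prespecified rule is meant to prevent both.

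**Working it through.** **The texts side by side**

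| Event preventing resection | Counts under 14.3 (literal) | Counts under 14.4 |
|---|---|---|
| Excessive toxicity | Yes | Yes |
| Progression seen on imaging | Yes | No |
| Liver metastasis found at surgery, not on imaging | Yes, by inference | No |
| Peritoneal metastasis found at surgery, not on imaging | No | No |
| Both sites found at surgery | Not addressed | No |

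The third row is an inference. Section 14.3 does not say outright that disease found at laparoscopy is progression, or that such a patient failed to proceed with surgery. But an exclusion for peritoneal disease is needed only if disease found at surgery would otherwise count. Naming one site leaves the other in the count.

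**Inputs**

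- Patients at the look: 20 (14.3 and 14.4).
- Trigger: more than 6, so 7 or more; 7/20 = 35%.
- Rate of occult liver disease: not in the documents. Assumed 2.5% to 10% of patients.
- Base rate of the other countable events: not in the documents. Assumed 10% to 30%.

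**The plan's own figure.** The documents give no operating characteristics for the stopping rule, so there is nothing to reproduce for it. The 82% power in 14.1 concerns pathologic complete response and does not bear on this point.

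**Formula.** With a countable rate p and 20 assessed patients,

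P(stop) = P(X ≥ 7) = Σ from k = 7 to 20 of C(20,k) p^k (1 − p)^(20−k).

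| p | P(stop) |
|---|---|
| 10% | 0.2% |
| 15% | 2.2% |
| 20% | 8.7% |
| 25% | 21.4% |
| 30% | 39.2% |
| 35% | 58.3% |
| 40% | 75.0% |

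**Effect of counting occult liver cases.** If the causes are mutually exclusive, p = base + occult liver rate.

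| Base | Liver not counted | +2.5 points | +5 points | +10 points |
|---|---|---|---|---|
| 10% | 0.2% | 0.8% | 2.2% | 8.7% |
| 20% | 8.7% | 14.3% | 21.4% | 39.2% |
| 30% | 39.2% | 48.9% | 58.3% | 75.0% |

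Under 14.3, the same rate of occult peritoneal disease leaves P(stop) in the second column. Under 14.4, neither site moves it.

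**A related mismatch within 14.4.** Its percentage criterion of 25–30% is 5 to 6 of 20 (0.25 × 20 = 5; 0.30 × 20 = 6), whereas its count needs 7. Any reconciliation has to deal with this too.

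**The case against.** The strongest objection is that 14.4 is the section devoted to stopping the study and it counts toxicity only. If 14.4 governs, occult disease at either site is irrelevant and the asymmetry disappears. That is correct, and it limits the point to 14.3. It does not remove it, because both sections are current text and neither yields to the other. It also rules out copying the 14.3 exclusion into 14.4, which has no progression term to exclude anything from.

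A second objection is that a patient found to have liver disease at laparoscopy has already entered operative exploration, so may not be someone unable to proceed with surgery. The wording allows that reading. Against it, 14.3 presents the look as one at the resection rate, and the peritoneal exclusion would then be redundant.

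A reader might infer three stronger things that the documents do not support:

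- That the sponsor meant to excuse every occult metastasis and left out the liver by mistake. The text shows only that no reason is given; intent is not stated.
- That the trial runs a 21% to 39% risk of closing wrongly. Those values need a 20% base plus 5 to 10 points of occult liver disease, and neither rate is in the documents. At a 10% base the corresponding values are 2.2% and 8.7%.
- That 14.3 is the only numeric stopping rule. Section 14.4 states the same threshold for different causes and adds a percentage.

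**Conclusion.** The point holds in limited form. Section 14.3 as written makes the stopping count depend on the site of an imaging-occult metastasis, although 9.2 handles the two sites identically. Section 14.4 conflicts with 14.3 on whether progression counts at all. The mismatch in the text is certain, apart from the inference that an occult liver case counts.

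Its size is illustrative only. Between countable rates of 10% and 30%, each extra 5 points moves the stopping probability one step through 0.2%, 2.2%, 8.7%, 21.4% and 39.2%. An extra 2.5 points on a 20% base gives 14.3%. These figures assume 20 assessed patients, independent outcomes and mutually exclusive causes. They show that the rule is sensitive to classification, not that closure is likely. The definition of the primary endpoint and the stated power are unaffected.

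**What to change.** Before the 20-patient look, reconcile 14.3, 14.4 and 9.2 into one statement of the rule, placed in one section and cross-referenced from the other. It should say:

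1. Whether progression counts, or toxicity alone.
2. How imaging-occult metastases found at surgery are handled, with liver and peritoneum treated alike and patients with both sites covered.
3. Which threshold applies, so that the percentage and the count in 14.4 agree.

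If the sponsor decides that 14.3 governs and keeps the exclusion, the exclusion should name both sites searched under 9.2. If 14.4 governs, the progression term and the exclusion in 14.3 should be removed. That choice is the sponsor's, and the documents do not settle it.

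The cost is a few words in an amendment. No additional data or patients are needed.

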2.2 Secondary Objectives

1. To describe the adverse events associated with FOLFIRINOX when administered preoperatively in patients with resectable pancreatic cancer.
2. To estimate the fraction of patients who can successfully undergo surgery after neoadjuvant chemotherapy.
3. To estimate the overall resectability rate, rate of R0 resection, disease free survival (DFS), overall survival (OS), overall response rate (ORR; complete response (CR) + partial response (PR)), and disease control rate (DCR; CR + PR + stable disease (SD)) after administration of FOLFIRINOX in patients with resectable pancreatic cancer.

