3.2 Secondary Outcome Measures

- Percentage of patients to undergo surgical resection after receiving neoadjuvant FOLFIRINOX
- Disease free survival and overall survival for patients with resected pancreatic cancer

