4.1 Inclusion Criteria

1. ≥ 18 years old at the time of informed consent
2. Able to provide written informed consent and HIPAA authorization
3. ECOG performance status of 0 or 1
4. Patient must be eligible for abdominal surgery

5. Cytologically or histologically confirmed adenocarcinoma of the pancreas that has been documented to be resectable by standardized radiographic criteria by a pancreatic surgeon
6. Women of childbearing potential definition (WOCBP) must have a negative serum or urine pregnancy test performed within 14 days prior to initiation of FOLFIRINOX. Any woman (regardless of sexual orientation, having undergone a tubal ligation, or remaining celibate by choice) is classified as WOCBP if she meets the following criteria:
 - a. Has not undergone a hysterectomy or bilateral oophorectomy; or
 - b. Has not been naturally postmenopausal for at least 24 consecutive months (i.e. has had menses at any time in the preceding 12 consecutive months).
7. WOCBP and men must agree to use adequate contraception prior, to study entry, for the duration of study participation, and 8 weeks after the end of treatment.
8. Patients must have adequate organ function as defined by the following laboratory values at study entry:
 - a. Hemoglobin ≥ 9 g/dL (transfusions are acceptable)
 - b. ANC $\geq 1.5 \times 10^9/L$
 - c. Platelets $\geq 100 \times 10^9/L$
 - d. Creatinine $\leq 1.5 \times$ ULN, or creatinine clearance ≥ 50 mL/min (estimated by Cockcroft-Gault or measured)
 - e. Total bilirubin $\leq 2 \times$ ULN
 - f. AST/ALT $\leq 3 \times$ ULN

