7. TREATMENT PLAN

7.1 Treatment Dosage and Administration

Patients on this trial will be treated with neoadjuvant FOLFIRINOX for 2 cycles (1 cycle = 28 days). Patients will receive FOLFIRINOX on an outpatient basis on days 1 and 15 of each cycle. Following neoadjuvant treatment, patients will undergo repeat imaging (CT or MRI) to be reassessed for resectability of the tumor. Further adjuvant treatment will be determined at the treating physician's discretion (i.e. chemoradiotherapy or adjuvant chemotherapy). It is important to note that post-neoadjuvant therapy is determined by the treating physician per their institutional guidelines and standard of care. While this study will collect data regarding disease progression and survival from the post-neoadjuvant period, this protocol does not dictate post-neoadjuvant treatment which may be done at other institutions.

For patients with an R1 resection, any chemoradiotherapy will be included in the 24 weeks of perioperative therapy. Chemoradiotherapy and the timing in which it will be given will be determined at the treating physician's discretion based on margin status and the patient's recovery. Furthermore, patients who receive chemoradiotherapy may also receive adjuvant chemotherapy; however, this will be based on the treating physician's discretion. Recommended radiosensitization will be through 5FU 200 mg/m²/Day continuous infusions M-F of each week or capecitabine 825 mg/m² PO BID M-F for the duration of radiation therapy. Patients who

receive adjuvant therapy will receive treatment based upon treating physician's discretion with a recommended duration of therapy lasting 6 months accounting for preoperative therapy.

The neoadjuvant FOLFIRINOX regimen starting doses are: oxaliplatin 85 mg/m², followed by leucovorin 400 mg/m² given simultaneously with irinotecan 180 mg/m², followed by 5FU 400 mg/m² bolus and then 2400 mg/m² (Table 1). Patients require a PORT, PICC or other IV access to allow administration of 5FU via a continuous infusion pump. All agents should be administered within SOC drug administration guidelines. Appropriate dose modifications for each agent are described in Section 9.0. See drug monographs/package inserts for full details on each agent.

Agent	Dose*	Route	Schedule
Oxaliplatin	85 mg/m ² in 250 cc D5W	IV before irinotecan	Day 1,15 of each 28 day cycle

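### Section 14.3 takes the surgery rate among patients with a resectable tumor without saying when; if this means at restaging, patients who became unresectable drop out and the rate is inflated

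*Combined protocol and SAP*

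**What the plan says.** Objective 2 in Section 2.2 is "To estimate the fraction of patients who can successfully undergo surgery after neoadjuvant chemotherapy". The matching outcome measure in Section 3.2 is "Percentage of patients to undergo surgical resection after receiving neoadjuvant FOLFIRINOX". Neither sets a condition on resectability.

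The analysis in Section 14.3 adds one: "the proportion of patients who are able to go through surgery among those who have resectable tumor will be calculated", with a 95% confidence interval. It does not say when resectability is judged.

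The protocol judges resectability on imaging at two points. At entry, criterion 5 in Section 4.1 requires disease "documented to be resectable by standardized radiographic criteria by a pancreatic surgeon". After chemotherapy, Section 7.1 says "patients will undergo repeat imaging (CT or MRI) to be reassessed for resectability of the tumor".

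The next bullet in Section 14.3, the rate of resectability, is "the proportion of patients who are able to undergo surgery with resection of their primary tumor (R0 vs R1) resection". It has no resectability condition, but its denominator is given only as patients. Neither bullet names an analysis set from Section 14.2, whereas the pathologic response and overall survival bullets both refer to 48 patients.

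**The concern.** When chemotherapy is given first in resectable disease, the main feasibility question is how many patients lose the chance of surgery. A patient whose tumor becomes unresectable during treatment is a failure on that question. If the denominator contains only patients still resectable at restaging, that patient is not counted at all. The rate is then conditional on a post-treatment outcome, and it looks better the more often the treatment fails in this way.

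Leaving the time point open is also a problem in itself. An analyst could defend either denominator after seeing the data, and the two results could differ by 10 points or more.

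**Working it through.** **The plan's own figure.** There is none to reproduce. The plan gives no target, expected value or power for the surgery rate. Its only power figure, 82%, concerns pathologic complete response and does not bear on this point.

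**When the condition has an effect.**
- Judged at entry: criterion 5 already requires it of everyone, so the denominator is all patients and the words exclude nobody.
- Judged at restaging: the denominator is the patients still resectable on repeat imaging, and those found unresectable leave it.

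The words do some work only on the second reading. That makes it the more natural one, but the text does not settle it.

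**Formula.** Let N be the patients in the study, P those found unresectable at restaging, O those not operated for other reasons, and S = N - P - O those operated.
- All patients: S/N.
- Resectable at restaging: S/(N - P).
- Ratio of the second to the first: N/(N - P). It does not depend on O and rises with P.

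**Inputs.** N = 48 is the planned enrolment (Sections 6 and 14.1). P and O are assumptions, because the plan gives neither. O is fixed at 4, and P is set at 5, 7 and 14.

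**Results.**

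| P | O | S | S/N | S/(N - P) | N/(N - P) | Gap (points) |
|---|---|---|---|---|---|---|
| 5 | 4 | 39 | 39/48 = 81.2% | 39/43 = 90.7% | 1.12 | 9.4 |
| 7 | 4 | 37 | 37/48 = 77.1% | 37/41 = 90.2% | 1.17 | 13.2 |
| 14 | 4 | 30 | 30/48 = 62.5% | 30/34 = 88.2% | 1.41 | 25.7 |

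For P = 7 the exact (Clopper-Pearson) 95% intervals are 62.7-88.0% and 76.9-97.3%. The all-patient rate falls by about 19 points down the table (81.2% to 62.5%), while the conditional rate falls by less than 3 (90.7% to 88.2%). The conditional rate therefore barely registers the loss of patients to unresectable disease.

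**Entry reading.** P is not subtracted, both rates are S/48, and the gap is 0.

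**The case against.** The strongest reply is that the trial population is, by definition, patients with resectable pancreatic cancer. The phrase may simply be a loose label for everyone enrolled. Section 14.3 is loosely worded elsewhere, so redundancy is weak evidence of intent. This stands. A reader might infer that the plan definitely removes patients who progress and so inflates the rate. The documents do not support that, because no time point is given and the entry reading produces no bias.

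Second, the neighbouring bullet on the rate of resectability, read plainly, is resected patients over all patients. A reader might infer that the loss of surgery would go unreported. That is not supported either, since the next bullet may well show it. But its denominator is not stated, and it would not correct the first bullet, which is the one that carries the name of the Section 3.2 outcome.

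Third, a reader might take the progression and intolerance figures in Section 1.3 (14% and 9%) as a forecast. They come from 21 patients with borderline resectable or locally advanced disease, whereas this trial enrols resectable disease only. Intolerance also need not mean no surgery: the study calendar gives a surgical evaluation to patients who discontinue chemotherapy. And only unresectability seen on imaging would remove a patient, so occult metastases first found at operation (Section 9.2) would stay in the denominator.

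Fourth, the interim rule does not settle the question. In Section 14.3 it reads "If >6 patients are not able to proceed with surgery due to excessive toxicity or progression", which counts progression as failure to reach surgery, but it excludes occult peritoneal disease found at surgery. Section 14.4 restates the rule with toxicity only. The two statements need reconciling in their own right, and an interim trigger need not share a definition with a final estimate.

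Finally, this is a descriptive secondary proportion with no test attached. That limits the consequence, but not the need for a denominator that answers the objective.

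**Conclusion.** The point holds in conditional form. The denominator in Section 14.3 has no time point. On the reading that gives its condition any effect, patients found unresectable at restaging are excluded, the rate is inflated by N/(N - P), and it departs from Sections 2.2 and 3.2. With 48 patients and 4 others not operated, the inflation is about 9 to 26 points for 5 to 14 such patients, and about 13 points for 7. These counts are assumed for illustration and are not estimates for this trial. On the entry reading the inflation is zero and only the wording needs attention. The change should be made before analysis because the stated rule, on its more natural reading, does not answer the plan's own objective.

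**What to change.** In Section 14.3, replace the denominator of the surgery rate with all registered patients who start FOLFIRINOX. Count patients who do not reach surgery because of progression, toxicity, refusal or death as not operated. State the same denominator for the rate of resectability. Since this set is not among those in Section 14.2, add it there or define it in the bullet. A rate among patients resectable at restaging may be kept if it is labelled supplementary and its denominator is reported.

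The cost is a sentence or two of text, with no new patients, visits or data. If the condition was meant to apply at restaging, the reported rate becomes less favourable. If it was meant to apply at entry, the change mainly makes the wording clear.

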9. STUDY PROCEDURES

9.1 EUS or CT-Guided Biopsy Procedure

Pancreatic cancer is commonly staged by the means of endoscopic ultrasound (EUS). This is a standard of care procedure which includes minimal sedation and upper endoscopy. A linear echoendoscope will be utilized to identify the pancreatic mass. A fine needle aspirate (FNA) or core biopsy will be performed at the same time. As with standard practice, biopsy will be performed with on-site cytology review to confirm malignancy. All diagnostic biopsies must be reviewed by the Pathology Department per the institutional guidelines.

If patients do not proceed to surgery after neoadjuvant treatment (may occur if the patient refuses surgery, is not eligible for surgery or has progression of disease), then an optional biopsy may be completed at the end of treatment. In these cases, a CT-guided biopsy will likely be performed. EUS biopsies are typically performed for patients who have localized disease while CT-guided biopsy is typically performed when metastatic disease is suspected.

Biopsies may be performed prior to patient enrollment as they are standard of care for pancreatic cancer diagnosis. Therefore, tissue samples being stored with the Pathology Department (i.e. archival tissue) in lieu of fresh tissue collection may be requested after enrollment to satisfy the baseline tissue collection requirement of this study. Additionally, it may be difficult to coordinate fresh tissue collect at the time of surgical resection (see below) or biopsy; therefore, archival tissue may also be collected to satisfy the post-neoadjuvant treatment tissue collection requirement of this study.

Additional details regarding tissue collection can be found in Section 12.1.

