11.3 Evaluation of best overall response

The best overall response is the best response recorded from the start of the treatment until disease progression/recurrence (taking as reference for PD the smallest measurements recorded since the treatment started). The patient’s best overall response assignment will depend on the findings of both target and non-target disease and will also take into consideration the appearance of new lesions.

Target Lesions	Non-Target Lesions	New Lesion?	Best Overall Response
-----------------------	---------------------------	--------------------	------------------------------

Protocol Version Date:
October 2, 2019

CR	CR	No	CR
CR	Non CR/ Non PD	No	PR
CR	Not evaluated	No	PR
PR	Non-PD or not all evaluated	No	PR
SD	Non-PD or not all evaluated	No	SD
Not all evaluated	Non-PD	No	NE
PD	Any	Yes or No	PD
Any	PD	Yes or No	PD
Any	Any	Yes	PD

Patients with a global deterioration of health status requiring discontinuation of treatment without objective evidence of disease progression at that time should be classified as having “symptomatic deterioration”. Every effort should be made to document the objective progression even after discontinuation of treatment.

In some circumstances it may be difficult to distinguish residual disease from normal tissue. When the evaluation of complete response depends on this determination, it is recommended that the residual lesion be investigated (fine needle aspirate/biopsy) to confirm the complete response status.

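### Section 3.2 gives DFS and OS for resected patients while 14.3 analyses OS in all 48; DFS runs from registration with no stated population and does not name pre-operative progression as an event

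*Combined protocol and SAP*

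**What the plan says.** Three places describe who is analysed.

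- Section 3.2 lists "Disease free survival and overall survival for patients with resected pancreatic cancer".
- Section 2.2 gives the same endpoints "after administration of FOLFIRINOX in patients with resectable pancreatic cancer", which is wider than resected.
- Section 14.3 takes OS as "time from registration to death for 48 patients with right censoring will be analyzed using Kaplan-Meier estimate", that is, the whole planned enrolment.

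For DFS, 14.3 sets the origin and the events: "time from registration to evidence of tumor recurrence (including clinical deterioration related to the underlying pancreatic cancer, as assessed by the investigator) or death", whatever caused the death. It asks for a Kaplan-Meier curve and a median with a 95% confidence interval. It states no DFS population and no DFS censoring rule.

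The protocol expects some patients not to be resected. Section 9.1 says this "may occur if the patient refuses surgery, is not eligible for surgery or has progression of disease". Section 9.2 adds: "Proof of metastatic cancer (i.e. stage IV cancer) will exclude patients from operative resection of the primary pancreatic cancer". Neither section says how such a patient enters the DFS analysis. The correlative part of 14.3 also relates biomarkers to PFS. The abbreviation list spells PFS out, but no section gives it a population, origin or event list.

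**The concern.** At registration the tumour is in place, so there is nothing yet to recur. A clock that starts there needs an event for patients whose disease advances before or at surgery. The definition supplies one only if the investigator records cancer-related clinical deterioration, or if the patient dies. Progression seen only on a scan, or metastases found at laparoscopy in a patient who feels well, are not named.

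Restricting the analysis to resected patients removes that problem and creates another. Nobody can be in the group without having reached surgery free of a disqualifying event, so the pre-operative weeks are guaranteed time.

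Two analysts could therefore report different DFS medians from the same data, and different OS medians if one follows 3.2 and the other 14.3. A single-arm median is usually read against other studies, so its origin and events need to be explicit.

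**Working it through.** **Plan's own figures.** The plan gives no design figure for DFS or OS. Its one design figure, 82% power for pathologic complete response (1% against 10%, 43 evaluable), reproduces with an exact binomial test: the cut-off is 3 or more responses, with type I error 0.009 and power 0.818. It does not depend on the DFS or OS definitions.

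**Reading 1: resected patients, clock from registration (3.2 with 14.3).** Inputs: two 28-day cycles with doses on days 1 and 15 of each (7.1), hence on days 1, 15, 29 and 43; surgery 4 ± 2 weeks after neoadjuvant treatment (9.2). Months are 30.4 days.

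- Counted from the last dose, 42 days after day 1: 42 + 14/28/42 = 56/70/84 days = 8/10/12 weeks = 1.8/2.3/2.8 months.
- Counted from the end of cycle 2 (day 56), 55 days after day 1: 55 + 14/28/42 = 69/83/97 days = 9.9/11.9/13.9 weeks = 2.3/2.7/3.2 months.

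The median from registration is roughly the median from surgery plus this interval. With an assumed 12.0 months from surgery, it is 14.3 (12.0 + 2.3) or 14.7 (12.0 + 2.7). Any gap between registration and day 1 adds to the interval; stopping chemotherapy early shortens it.

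**Reading 2: all registered patients.** The documents give none of the rates needed, so this is an illustration. Let *f* be the share whose disease progresses before or at surgery, *w* the time to surgery or restaging, *m* the median post-operative DFS (12 or 15 months), and *d* the median time from progression to the first event that the definition does count. All times after *w* are exponential.

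- All progressors scored at *w*: (1 − f)·2^(−(t−w)/m) = 0.5, so t = w + m·log2[2(1 − f)].
- None scored at *w*: (1 − f)·2^(−(t−w)/m) + f·2^(−(t−w)/d) = 0.5, solved numerically.

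Example with f = 10%, m = 12, w = 2.7. All scored: 2.7 + 12 × 0.848 = 12.9 months. None scored: 14.4 if d = 9 (gap 1.5), and 13.2 if d = 3 (gap 0.3).

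Lengthening of the median in months, none scored minus all scored, over m = 12 and 15:

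| f (of 48) | d = 1 | d = 3 | d = 6 | d = 9 | d = 12 |
|---|---|---|---|---|---|
| 5% (about 2) | 0.0 | 0.1 | 0.4-0.5 | 0.7 | 0.9 |
| 10% (about 5) | 0.0 | 0.2-0.3 | 0.9-1.0 | 1.5 | 1.8-1.9 |
| 12.5% (6) | 0.0 | 0.3-0.4 | 1.2-1.3 | 1.9 | 2.3-2.5 |
| 20% (about 10) | 0.0 | 0.7-0.9 | 2.2 | 3.2-3.3 | 3.9-4.2 |

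Columns d = 1 and 3 represent clinical deterioration being recorded soon after progression. Columns 6 to 12 represent waiting for death. The choice of surgery window does not change the gaps.

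The documents do not pin down *f*. The 2 of 16 and 3 of 21 in section 1.3 are progression on treatment in other studies. The interim limit in 14.3 counts patients "not able to proceed with surgery due to excessive toxicity or progression (not including occult metastatic peritoneal disease that was found during surgery", so it mixes in toxicity and leaves out part of the progression.

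**Scale.** With 48 patients, full follow-up and a median of 14.7 months, the order-statistic 95% interval is about 10 to 21 months.

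**The case against.** Several points on the other side stand.

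- *Resected* in 3.2 may be a slip for *resectable*, the word used in 2.2. If so, reading 1 disappears. The sections still disagree as written and need reconciling.
- OS in 14.3 has an origin, event, population, censoring and estimator. A reader might infer that the OS analysis is defective. It is not; only 3.2 is out of step.
- The definition counts cancer-related deterioration. A reader might infer that every pre-operative failure stays disease-free until death, and take the 9-month column as what the plan produces. The text does not support that: prompt recording of deterioration brings the gap close to zero. What remains is asymptomatic failure.
- A reader might also infer that recurrence was meant to exclude progression. The documents do not settle this. Section 11.3 takes best response "from the start of the treatment until disease progression/recurrence", and that pairing fits interchangeable use as well as separate terms. The interim rule does treat progression and occult peritoneal disease as distinct. Section 11.2 says when a new lesion is progression and how to date it, so what is missing is the link to DFS, not progression criteria.
- The endpoints are descriptive, with no comparator or decision rule, and the illustrated shifts lie within sampling error.

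**Conclusion.** The point holds in limited form. Sections 2.2, 3.2 and 14.3 do not agree on the population, and DFS in 14.3 has no stated population, no censoring rule and no explicit treatment of disease that advances before or at surgery.

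The 1.8-3.2 months under the resected reading follow from the planned schedule and need no outcome assumptions. The all-registered effect ranges from about nil to 4.2 months, depending on a failure rate and an event delay that the documents do not give; its lower part (0-0.9 month) applies if deterioration is recorded within a median of 1-3 months. Sampling error does not remove the problem, because the shift always runs in the favourable direction.

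The primary endpoint, its power, and OS as written in 14.3 are unaffected. This should be corrected before analysis, but it does not threaten the trial's main result.

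**What to change.** 1. In 3.2, state OS in all enrolled patients from registration, as 14.3 already does.
2. Rename the registration-based endpoint event-free survival and give its population as all enrolled patients. Events: progression before surgery (including progression that precludes resection), metastatic disease found at laparoscopy or laparotomy, recurrence after resection, cancer-related clinical deterioration as now written, and death. Patients left unresected without progression stay in follow-up. Patients without an event are censored at the last disease assessment.
3. If DFS in resected patients is kept, time it from the date of surgery.
4. Make PFS in the correlative analyses refer to the endpoint in item 2.

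The cost is mostly wording. Section 7.1 already commits to collecting progression and survival after neoadjuvant treatment, and the interim rule already requires identifying patients who miss surgery through progression. The additions are the date and basis of pre-operative progression. Medians may be slightly less favourable, and follow-up at 3-6 months in years 1-3 (section 10, footnote 9) keeps the dating of later events coarse.

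Separately, section 7.1 and footnote 5 of the study calendar differ on whether restaging imaging is routine or discretionary. The sponsor should reconcile them.
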